## SCHEMA

Patients with PAX8-PPARgamma – positive thyroid cancer that is either metastatic s/p thyroidectomy and radioiodine (if appropriate), or is locally advanced/recurrent not a candidate for further surgery, radioiodine or external beam radiotherapy

## **1. OBJECTIVES**

### **1.1 Primary Objectives**

Determine the overall response (complete and partial response) rates of patients with PAX8-PPARgamma fusion gene-positive thyroid carcinomas treated with pioglitazone.

### **1.2 Secondary Objectives**

Determine if pioglitazone decreases serum thyroglobulin in patients with thyroid carcinomas that contain the PAX8-PPARgamma fusion gene.

Measure toxicities experienced by patients with PAX8-PPARgamma fusion gene-positive thyroid carcinomas treated with pioglitazone.

### **1.3. Correlative Objectives (Optional)**

Determine (by MRI) if pioglitazone induces lipid accumulation in thyroid carcinomas that contain the PAX8-PPARgamma fusion gene.

Define predictive markers of response or insensitivity to pioglitazone. Unstained tumor tissue slides from archival paraffin blocks, fresh biopsy specimens from measurable metastases, and blood samples (serum and peripheral blood cells) will be collected on enrolled patients who consented for the optional correlative studies. These will be used to identify factors that predict efficacy of pioglitazone. Analyses may include measures of expression of specific RNAs and proteins, and DNA sequence analysis.

Determine if pioglitazone induces a clinically significant level of radioiodine uptake in the residual thyroid carcinoma, and if so, whether there is a therapeutic response to radioiodine. This will be addressed in a separate follow-up protocol available to subjects completing this study.

## **2. BACKGROUND**

### **2.1 Study Disease**

Follicular carcinoma and follicular variant of papillary carcinoma (together called follicular-patterned thyroid carcinomas) constitute about 15% of thyroid carcinomas. Approximately one-third of follicular carcinomas (1, 2), as well as a subset of follicular variant of papillary carcinomas that has been reported to vary from 0 – 38% (3, 4), contain a chromosomal translocation that fuses the genes encoding PAX8 and PPARgamma, resulting in the production of a PAX8-PPARgamma fusion protein (PPFP).

In general the therapy of thyroid cancer is surgical thyroidectomy followed by radioactive iodine (5). These therapies are effective in the majority of cases, resulting in a 10 year survival of ~85% in follicular carcinoma (6). However, distant metastases occur, primarily in the lung and less commonly in organs such as liver and bone. Metastatic disease is not always responsive to radioiodine – in some cases the tumor concentrates radioiodine but not at sufficient levels to cause a response, and in other cases the metastases do not concentrate radioiodine. There is no accepted chemotherapy or other therapy for these patients, and for these reasons, the median survival of AJCC stage IV follicular carcinoma is only ~4 years (6).

## 2.2 Rationale

PPFP is a fusion protein between two transcription factors, PAX8 and PPARgamma (1). PAX8 is required for thyroid development, and in the mature thyroid, it drives the expression of thyroid specific genes. PPARgamma is expressed at very low levels in the normal thyroid and has no known function in that organ. PPARgamma is the master transcriptional regulator of adipogenesis, and in the mature adipocyte it drives the expression of adipocyte specific genes (7). PPARgamma is a nuclear hormone receptor. In clinical practice, it is best known because agonist ligands (thiazolidinediones) are insulin sensitizers (8). Thus, thiazolidinediones are commonly used to treat type 2 diabetes mellitus. One such drug, pioglitazone (trade name Actos® or generic equivalent), will be used in this study.

PPFP contains the entirety of PPARgamma, and hence thiazolidinediones also bind to PPFP. In cell culture transfection studies, we have shown that a PPARgamma-responsive promoter is induced by PPFP plus thiazolidinedione, similar to the action of PPARgamma plus thiazolidinedione (9). Furthermore, human PPFP thyroid cancers have increased expression of PPARgamma responsive genes, relative to PPFP-negative thyroid cancers (9).

We have produced an animal model of follicular thyroid carcinomas by creating mice that have both thyroid-specific expression of PPFP and thyroid-specific deletion of the tumor suppressor Pten (hereafter denoted PPFP;PtenΔ mice) (10). PPFP expression alone causes mild benign hyperplasia, and PtenΔ alone causes a much greater degree of benign hyperplasia but no tumors. In contrast, the combined PPFP;PtenΔ mice develop thyroid cancer with local invasion into soft tissues, vascular invasion, and distant metastases. The reason we combined PPFP expression with PtenΔ is that we previously found that human PPFP cancers have high expression of phosphorylated AKT, which is not replicated in mice by PPFP expression alone. Pten is a negative regulator of AKT phosphorylation, so Pten deletion is known to increase phosphorylated AKT levels. We treated PPFP;PtenΔ mice with pioglitazone or control diet beginning at 2 months of age for 10 weeks. Ten mice received pioglitazone and 12 mice served as controls. Ultrasound measurements showed that, over the 10 week treatment period, the control mouse thyroids grew 3-fold in size and the pioglitazone-exposed thyroids decreased to less than half their starting size. At the end of the study, the control mouse thyroids were 7 fold larger

(by weight) than the pioglitazone mouse thyroids. Seven of the 12 control mice had distant metastases, whereas none of the pioglitazone mice had metastases ( $P < .005$ ).

Perhaps the most striking result pertained to the histology of the thyroid glands in the pioglitazone treated mice. The thyroid cells were laden with lipid droplets, suggesting that pioglitazone caused a trans-differentiation of the thyroid cells into adipocyte-like cells. These cells express PPFP and the thyroid specific markers TTF-1 and thyroglobulin, indicating they are thyroid in origin. However, we also examined the expression of 17 adipocyte PPARgamma target genes, and all 17 were induced in the pioglitazone-treated thyroids.

To test whether this adipogenic response is dependent on PPFP, we also studied Pten $\Delta$  mice that do not have PPFP. Eleven Pten $\Delta$  mice received pioglitazone and 15 served as controls. Pioglitazone had no effect on either thyroid size or histology.

We conclude that pioglitazone has a remarkable therapeutic effect in this PPFP;Pten $\Delta$  mouse model of thyroid cancer, and that the effect requires the expression of PPFP. The effect involves the trans-differentiation of PPFP expressing thyroid cells into adipocyte-like cells, which reflects the PPARgamma-like action of PPFP in the presence of pioglitazone, a PPARgamma ligand. If similar activity is seen in human PPFP thyroid cancers, pioglitazone should have a powerful salutary effect on this disease. Furthermore, pioglitazone is commonly used to treat type 2 diabetes, and it has a well established safety profile in that setting in chronic use. Therefore, dosing in this study will adhere to the levels for the approved indication.

The duration of therapy in the proposed clinical trial is 24 weeks. The rationale for this duration is as follows. In the mouse model of PPFP thyroid cancer, 10 weeks of pioglitazone decreased thyroid diameter to less than half that of untreated mice, and completely eliminated metastatic disease. Therefore, we believe that a response in patients should be measurable by 24 weeks of therapy, if a response is to occur.

### **2.3 Correlative Studies Background**

Serum thyroglobulin levels will be measured. Thyroglobulin is a well established tumor marker in thyroid cancer. Serial serum thyroglobulin measurements are part of the accepted standard of care for thyroid cancer management (5).

Optional for enrolled patients who consent: MRI will be used to assess fat content of the cancer metastases. MRI is an accepted non-invasive method to assess tissue fat content. Our mouse tumor model data indicate that pioglitazone causes a lipogenic response (i.e. the mouse tumors accumulate lipid droplets), which reflects the PPAR $\gamma$ -like action of PPFP. To assess feasibility, we performed thyroid MRIs on two PPFP;Pten $\Delta$  mice that were treated with pioglitazone and two that were not. Thyroid fat content was 13% in the two control diet mice, and 25 to 26% in the pioglitazone-treated mice. This optional MRI consent will allow us to assess whether a similar effect occurs in patients, and will provide another index of a response to pioglitazone.

Optional for enrolled patients who consent: Unstained tumor tissue slides from archival paraffin blocks, and/or fresh biopsy of tumor metastases, and/or peripheral blood (sera and/or DNA) will be collected and stored for potential analyses of tumor markers that may predict response or insensitivity to pioglitazone.

Optional radioiodine scan, and potentially radioiodine therapy, at the end of pioglitazone therapy. In non-PPFP thyroid carcinomas, thiazolidinediones have been shown to induce radioiodine uptake in some patients with otherwise non-iodine avid metastases, although in general the level of uptake has been clinically insignificant (11, 12), with rare exception (13, 14). It seems unlikely that pioglitazone would induce clinically useful radioiodine uptake in PPFP carcinomas, since in the mouse model the thyroid cells differentiate toward adipocytes, not thyrocytes. However, radioiodine uptake in patients should be determined to formally address this question. Patients with clinically significant uptake would be considered for radioiodine therapy, if clinically appropriate. This will be addressed in a separate follow-up protocol available to subjects completing this study.

### **3. PATIENT SELECTION**

#### **3.1 Inclusion Criteria**

3.1.1 Patients must have histologically confirmed thyroid carcinoma with the PAX8-PPARgamma translocation.

Refractory to radioactive iodine (RAI) as defined by: the tumor does not concentrate RAI; or the patient has had RAI within the last 16 months and has had progression despite that RAI; or the last RAI treatment was >16 months ago and the patient progressed after at least two RAI treatments; or the patient has received RAI treatments with a cumulative RAI dose of  $\geq 22.2$  GBq (600 mCi)

Not a candidate for surgery or RAI therapy with curative intent.

Lesions that would be treated by external beam radiation therapy (EBRT) based on standard of care can be so treated, but then cannot be used as target lesions unless there has been progression of the lesion since treatment (see criteria 3.1.7).

3.1.2 Measurable disease by RECIST 1.1 criteria.

3.1.3 Disease progression in the past 14 months.

3.1.4 Availability of histological material (primary tumor or metastases) for review of the diagnosis and demonstration of PAX8-PPARgamma fusion gene.

- 3.1.5 Adequate TSH suppression (<0.5 mIU/L)
- 3.1.6 Prior chemotherapy or surgery must have been completed at least 28 days prior to registration, and all toxicities must have resolved.
- 3.1.7 Prior radioactive iodine must have been completed at least 6 months prior to registration, or there must be documented disease progression since such therapy if it was within 6 months. Sites that have received EBRT must have disease progression post-EBRT to be used as sites of measurable disease.
- 3.1.8 Age  $\geq$ 18 years.
- 3.1.9 Life expectancy of greater than 6 months.
- 3.1.10 ECOG performance status 2 or less.
- 3.1.11 Patients must have normal organ function as defined below:
  - AST(SGOT)/ALT(SGPT)  $\leq$ 2.5 X institutional upper limit of normal (within 1 month of study Day 1)
- 3.1.12 Patients must be able to consume oral medications.
- 3.1.13 Women of childbearing potential must have a negative pregnancy test at baseline prior to receiving any study drug and must practice effective contraception while on study. (Pregnant or lactating patients are excluded).
- 3.1.14 All patients must sign an informed consent prior to enrollment.

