## **3.2 Exclusion Criteria**

- 3.2.1 Patients may not be receiving any other investigational agents.
- 3.2.2 Patients with known untreated brain metastases.
- 3.2.3 History of allergic reactions attributed to compounds of similar chemical or biologic composition to pioglitzaone.
- 3.2.4 Diagnosis of diabetes mellitus or current therapy with any drugs used to treat diabetes mellitus, including but not limited to insulin, sulfonylureas, metformin, rosiglitazone (Avandia), and pioglitazone (Actos) within 14 days of study Day 1
- 3.2.5 Therapy with rosiglitazone (Avandia) or pioglitazone (Actos) at any time since the diagnosis of thyroid cancer.

- 3.2.6 Uncontrolled intercurrent illness including, but not limited to, ongoing or active infection, congestive heart failure, unstable angina pectoris, or cardiac arrhythmias.
- 3.2.7 Pregnant women are excluded from this study because pioglitazone is a U.S. Food and Drug Administration Pregnancy Category C drug. Because there is an unknown but potential risk for adverse events in nursing infants secondary to treatment of the mother with pioglitazone, breastfeeding should be discontinued if the mother is treated with pioglitazone.
- 3.2.8 No concurrent radiotherapy or chemotherapy may be given to the patient during the administration of the study drug.
- 3.2.9 Patients with uncontrolled malabsorption syndromes.
- 3.2.10 Patients with a history of congestive heart failure of any New York Heart Association class.
- 3.2.11 Any medical or psychiatric illness which, in the opinion of the principal investigator, would compromise the patient's ability to tolerate this treatment regimen.
- 3.2.12 Use of rifampin (strong CYP2C8 inducer) within 14 days of study Day 1.
- 3.2.13 Other current malignancy than the disease under study.
- 3.2.14 Grade 2 or worse edema within 14 days prior to study Day 1, per CTCAE v4.

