## **4. TREATMENT PLAN**

### **4.1 Pioglitazone Administration**

This study will be conducted under an exemption of IND (# 113,492) granted by the FDA. Pioglitazone will be obtained from an outpatient pharmacy using a prescription issued by a study investigator.

Drug information is available in the drug package insert (See link in Appendix D).

Treatment will be administered on an outpatient basis. Reported adverse events and potential risks are described in Section 6. Appropriate dose modifications for

pioglitazone are described in Section 5. No investigational or commercial agents or therapies other than those described below may be administered with the intent to treat the patient's malignancy.

Pioglitazone will be administered once daily without regard to meals. The initial dosage will be 30 mg daily, increased to 45 mg after 4 weeks unless side effects require otherwise.

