#### 4.7 Study Calendar

	Pre-Study	Day 1	Wk 2	Wk 4	Wk 6	Wk 8	Wk 10	Wk 12	Wk 14	Wk 16	Wk 18	Wk 20	Wk 24/ EOT	Wk 28	Post treatment
Pioglitazone a		X													
Informed consent	X														
Demographics	X														
Medical history	X														
Concurrent meds	X														
Physical exam	X							X					X		
Vital signs	X							X					X		
Height	X														
Weight b															
Performance status	X							X					X		
Serum chemistry cd	X	X g				X				X			X		
CBC d	X	X g				X				X			X		
Thyroid blood tests de	X	X g					X						X		
β-hCG df	X														
Adverse event evaluation h	X		X	X				X			X		X		X
Tumor related imaging i	X							X					X	X	
Other correlative studies j	X												X		

a: Dose per protocol; orally administered once daily for 24-28 weeks..

b: Weight obtained at each study site visit and once/week on each subject's same home scale.

c: Pre-Study and Day 1 chemistries: bicarbonate, BUN, chloride, creatinine, glucose, potassium, SGOT[AST], sodium. At weeks 8, 16, 24: glucose, AST.

d: Blood tests can be performed locally.

e: TSH, Free T4, thyroglobulin, thyroglobulin antibodies. All thyroglobulin measurements are to be performed in the same laboratory. Serum thyroglobulin will not be used as a response parameter if endogenous antibodies invalidate the measurement.

f: Pregnancy test in women of childbearing potential only.

g: Within 1 month prior to administration of protocol therapy. Pre-Study assessments if within 1 month will suffice.

h: Adverse events evaluations at weeks 2, 4, 18 and post treatment (within 4 weeks and at 6 months) will be by telephone.

i: Baseline CT or MRI scans must be done within 4 weeks prior to the start of therapy. Baseline CT includes neck, chest and abdomen. Follow-up imaging for disease response is at sites of disease detected at baseline and must include abdomen in cases of elevated AST to evaluate for liver metastases. Week 28 confirmatory CT for patients who need such for RECIST criteria confirmation. Baseline MRI includes: areas with lesions on CT for which there is reasonable diagnostic uncertainty that may be clarified by MRI; and/or brain if clinically indicated.

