### **8.2 Response Criteria (using tumor related imaging CT)**

#### **8.2.1 Evaluation of Target Lesions**

Complete Response (CR): Disappearance of all target lesions

Partial Response (PR): At least a 30% decrease in the sum of the longest diameter (LD) of target lesions, taking as reference the baseline sum LD

Progressive Disease (PD): At least a 20% increase in the sum of the LD of target lesions, taking as reference the

		smallest sum LD recorded since the treatment started or the appearance of one or more new lesions
Stable Disease (SD):		Neither sufficient shrinkage to qualify for PR nor sufficient increase to qualify for PD, taking as reference the smallest sum LD since the treatment started
8.2.2 Evaluation of Non-Target Lesions		
Complete Response (CR):	Disappearance of all non-target lesions and serum tumor marker (thyroglobulin) level $\leq 0.5$ ng/mL	
Incomplete Response/ Stable Disease (SD):	Persistence of one or more non-target lesion(s) and/or serum tumor marker (thyroglobulin) level $> 0.5$ ng/mL	
Progressive Disease (PD):	Appearance of one or more new lesions and/or unequivocal progression of existing non-target lesions	

Although a clear progression of “non-target” lesions only is exceptional, the opinion of the treating physician should prevail in such circumstances, and the progression status should be confirmed at a later time by the review panel (or Principal Investigator).

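### No rule requires permitted EBRT to end before baseline thyroglobulin, so a radiation-related fall could be summarized as change on pioglitazone

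*Combined protocol and SAP*

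**What the plan says.** Section 3.1.1 expressly allows EBRT: "Lesions that would be treated by external beam radiation therapy (EBRT) based on standard of care can be so treated". An irradiated lesion may then serve as a target only if it has since progressed, and 3.1.7 repeats this for measurable sites.

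Washouts that apply to the patient are set for other therapies. For chemotherapy and surgery, 3.1.6 says "Prior chemotherapy or surgery must have been completed at least 28 days prior to registration, and all toxicities must have resolved". For radioiodine, 3.1.7 asks for six months, or documented progression since. The only patient-level limit on radiotherapy is 3.2.8: "No concurrent radiotherapy or chemotherapy may be given to the patient during the administration of the study drug".

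The study calendar (4.7) lists thyroid blood tests, including thyroglobulin, at Pre-Study and at Day 1. Footnote g qualifies the Day 1 entry: "Within 1 month prior to administration of protocol therapy. Pre-Study assessments if within 1 month will suffice".

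The first secondary objective (1.2) is "Determine if pioglitazone decreases serum thyroglobulin in patients with thyroid carcinomas that contain the PAX8-PPARgamma fusion gene". Section 9.2 handles it descriptively: before-and-after summaries for all patients and by response group, plus individual profile plots. Thyroglobulin is reviewed for the 12 months before enrollment. The only stated ground for setting a value aside is interference from antibodies (8.3 and calendar footnote e).

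**The concern.** The EBRT rule works at the level of the lesion. It keeps irradiated disease out of the target sum, which is what the RECIST endpoint needs. Serum thyroglobulin reflects all the patient's disease, so a rule about which lesions may be measured cannot protect it.

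Two sequences break no criterion. In the first, baseline thyroglobulin is drawn, a non-target lesion is irradiated, and pioglitazone starts. In the second, EBRT ends just before the draw and its effect on thyroglobulin appears later. In either case a fall caused by radiation would sit inside the baseline-to-week-12 and baseline-to-week-24 changes. There is no control arm to show what would have happened without the drug. What is at stake is how the thyroglobulin objective is read in a trial of 14 to 15 patients.

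**Working it through.** **The plan's own figure.** The nearby stated number is the 87% power in 9.1. Inputs: 14 evaluable patients, 5% null rate, 40% alternative, two-sided 0.05. By the exact binomial, P(X ≥ 3 | 0.05) = 0.0301, above 0.025, and P(X ≥ 4 | 0.05) = 0.0042. The rule is therefore 4 or more responses, with power P(X ≥ 4 | 0.40) = 0.876. The figure reproduces. No EBRT timing enters it, so nothing below changes it.

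**The rules side by side.**

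| Prior therapy | Interval before registration | Toxicities resolved | Other limit |
|---|---|---|---|
| Chemotherapy, surgery | 28 days (3.1.6) | required | chemotherapy barred on drug (3.2.8) |
| Radioiodine | 6 months, or progression since (3.1.7) | not stated | none used here |
| EBRT | none | not stated | target-lesion rule (3.1.1, 3.1.7); barred on drug (3.2.8) |

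**Longest gap between baseline draw and last EBRT fraction.** Count days from Day 1, take the month in footnote g as 31 days, and assume registration is no later than Day 1.

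- EBRT: the draw can be as early as day −31, and EBRT need only stop by Day 1. The gap is at most 31 days.
- Chemotherapy or surgery: completion is no later than day −28, so the gap is at most 31 − 28 = 3 days.
- If thyroglobulin is drawn on Day 1 itself, the gap is 0 and the first sequence disappears. The second remains.

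**That gap as a share of the thyroglobulin interval.**

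- To week 12 (84 days): 31/(31 + 84) = 31/115 = 27.0%. With the ±1 week window: 31/122 = 25.4% to 31/108 = 28.7%.
- To week 24 (168 days): 31/(31 + 168) = 31/199 = 15.6%. With the window: 31/206 = 15.0% to 31/192 = 16.1%.

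These are outer bounds on calendar time. They do not measure bias.

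**Weight of one patient.** In a mean over 14 patients, one carries 1/14 = 7.1%. At the hoped-for 40% response, 0.40 × 14 = 5.6, so about 6 responders and 8 non-responders. One patient then carries 1/6 = 16.7% or 1/8 = 12.5% of a by-response mean.

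**Size of the fall.** With no drug effect, the apparent fall in one affected patient equals the share of serum thyroglobulin coming from the irradiated lesion times the proportion of that output removed. The documents give neither. Purely as an assumption, 10% × 25% = 2.5% and 50% × 75% = 37.5%. If either factor is zero, so is the fall.

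**Primary endpoint.** An irradiated lesion stays out of the target sum unless it has since progressed. Thyroglobulin enters response only through non-target complete response in 8.2.2: "Disappearance of all non-target lesions and serum tumor marker (thyroglobulin) level" at or below 0.5 ng/mL. Under 8.2.3, target CR is CR if the non-target criterion is met and PR if it is not (short of progression). Section 9.2 counts both as response, so a thyroglobulin fall cannot change responder status.

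**The case against.** Much of the case on the other side stands.

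- **The Day 1 draw.** The calendar schedules thyroid tests on Day 1. The draw-then-irradiate sequence needs an earlier draw to be substituted under footnote g. That is right, and it makes 31 days an edge case, but the substitution is allowed.
- **The population.** The Schema describes locally advanced or recurrent patients as not candidates for EBRT. That confines the exposure mainly to metastatic patients. It does not remove it, because 3.1.1 permits EBRT in terms.
- **The bar in 4.1.** It says "No investigational or commercial agents or therapies other than those described below may be administered with the intent to treat" the malignancy. This sits in the treatment plan and names no start before Day 1, so it does not clearly cover the pre-treatment weeks.
- **The analysis is descriptive.** There is no thyroglobulin test in 9.2, and the 12-month look-back and profile plots show each patient's course. A plot can show a fall but cannot separate EBRT from drug without the EBRT date.

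A reader might infer four stronger things that the documents do not support:

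- **Percentages as bias.** The 27% and 16% above are shares of time and say nothing about the size of any fall.
- **A new baseline scan.** Footnote i says "Baseline CT or MRI scans must be done within 4 weeks prior to the start of therapy", so EBRT could follow the CT by up to 28 days. Because an irradiated lesion cannot be a target without later progression, a repeat CT would burden the patient for almost no gain.
- **EBRT would go unrecorded.** The calendar takes medical history only at Pre-Study, but the case report form is not in the documents, so this cannot be confirmed.
- **A distorted toxicity table.** The calendar has a Pre-Study adverse event evaluation, and 6.2 requires attribution. Both guard against counting radiation effects as drug toxicity.

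**Conclusion.** The gap is in the text and the point holds, as a minor one. EBRT to a non-target lesion, mainly in metastatic patients, may fall between baseline thyroglobulin and Day 1 or end just before baseline. Section 9.2 would summarize any resulting fall as change on pioglitazone. Exposure is at most 31 days before Day 1, against 3 days for therapies that 3.1.6 does cover. This assumes a 31-day month and registration no later than Day 1.

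The consequence is limited to the descriptive secondary thyroglobulin endpoint. How often this would happen, and how large the fall would be, cannot be taken from the documents; the effect may be zero. A reader might go further and suspect the response rate, but the target-lesion rule and the counting of both CR and PR as response do not support that. Sample size and power stand as written.

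**What to change.** 1. In 3.1.6, add EBRT to the 28-day and toxicity-resolution rule, and allow none between registration and Day 1.
2. In footnote g, require baseline thyroglobulin to be drawn after the last EBRT fraction, using the Day 1 draw already in the calendar where needed. This also closes the 3 days that the 28-day rule alone would leave.
3. A fall may continue beyond 28 days, so record the date of the last EBRT fraction and mark these patients in the profile plots planned in 9.2.

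Leave footnote i as it is; a repeat baseline CT is not warranted.

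The cost is a few words in two places and one recorded date. For the occasional patient irradiated shortly before entry, it also means a short registration delay or one repeat blood draw.
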